Appendix 2 Clinical Laboratory Tests

The following clinical laboratory assessments will be performed:

Serum Chemistry

- Sodium •
- Potassium •
- Chloride •
- Bicarbonate •
- Calcium •
- Magnesium •
- Phosphate •
- Creatinine •
- Urea Nitrogen ۰

Hematology

[figure not shown]
- Hemoglobin •
- Hematocrit •
- Platelets •

Urinalysis

- pН
- Creatinine

Glucose •

- Albumin •
- Bilirubin ٠
- Alkaline phosphatase •
- Alanine Aminotransferase •
- Aspartate Aminotransferase •
- Triglycerides •
- Cholesterol •
- LDL Cholesterol •
- HDL Cholesterol • USEONIN
- RBC •
- White blood cell count with differential

Appendix 3 Adverse Events: Definitions and Procedures for Recording, Evaluating, Follow-Up, and Reporting

Appendix 3.1 Adverse Event Definitions

An AE is any untoward medical occurrence in a clinical investigation subject administered a pharmaceutical product and that does not necessarily have a causal relationship with this investigational product or medicinal product. An AE can therefore be any unfavorable and unintended sign (including a clinically significant laboratory finding), symptom, or disease temporally associated with the use of a medicinal (investigational) product, whether or not causality is suspected (ICH Guidance E2A 1995).

Treatment-emergent Adverse Event

A TEAE is defined as any event emerging or manifesting at or after the initiation of treatment with an investigational product or medicinal product or any existing event that worsens in either intensity or frequency following exposure to the investigational product or medicinal product.

Serious Adverse Event

A SAE is any untoward clinical manifestation of signs, symptoms or outcomes whether considered related to investigational product or not and at any dose:

- Results in death
- Is life-threatening. Note: The term "life-threatening" in the definition of "serious" refers to an event in which the subject was at risk of death at the time of the event; it does not refer to an event which hypothetically might have caused death if it was more severe.
- Requires inpatient hospitalization or prolongation of hospitalization. Note: Hospitalizations that are the result of elective or previously scheduled investigations procedures or surgery for pre-existing conditions and have not worsened after initiation of treatment should not be classified as SAEs.

For example, an admission for a previously scheduled ventral hernia repair would not be classified as an SAE; however, complication(s) resulting from a hospitalization for an elective or previously scheduled surgery that meet(s) serious criteria must be reported as SAE(s).

- Results in persistent or significant disability/incapacity
- Results in a congenital abnormality/birth defect
- Is an important medical event. Note: Important medical events that may not result in death, be life-threatening, or require hospitalization may be considered an SAE when, based upon appropriate medical judgment, they may jeopardize the subject and may require medical or surgical intervention to prevent 1 of the outcomes listed in this definition. Examples of such medical events include bronchospasm associated with anaphylaxis requiring intensive treatment in an emergency room or at home; blood dyscrasias or convulsions that do not result in inpatient hospitalization; the development of drug dependency or drug abuse; and reviewed and confirmed seroconversion for human immunodeficiency virus (HIV), hepatitis A virus (HAV), hepatitis B virus (HBV), hepatitis C virus (HCV), hepatitis E virus (HEV), or parvovirus B19 (B19V).

Unexpected Adverse Event

An unexpected adverse event is an AE whose nature, severity, specificity, or outcome is not consistent with the term, representation, or description used in the Reference Safety Information (RSI). "Unexpected" also refers to the AEs that are mentioned in the investigator's brochure as occurring with a class of drugs or as anticipated from the pharmacological properties of the product, but are not specifically mentioned as occurring with the particular product under investigation.

The expectedness of AEs will be determined by the sponsor using the investigator's brochure as the RSI. This determination will include considerations such as the number of AEs previously observed, but not on the basis of what might be anticipated form the pharmacological properties of a product.

Suspected Unexpected Serious Adverse Reaction

A Suspected Unexpected Serious Adverse Reaction is defined as any suspected adverse reaction Jercial USE OF to study treatment (ie, including active comparators) that is both serious and unexpected.

The event(s) must meet all of the following:

- Suspected adverse reaction
- Serious
- Unexpected
- Assessed as related to study treatment

Infusion-Related Reactions

Definition of Infusion-Related Reactions

Infusion-related reactions will be defined as an AE that 1) begins either during or within 24 hours after the start of the infusion and 2) is judged as related to study treatment. Adverse events that are considered IRRs will be noted as such in the subject's source documentation. Other AEs that occur prior to an infusion, along with AEs associated with protocol-defined testing and assessments (laboratory testing and physical examinations) that were performed prior to an infusion will not be defined as IRRs.

A list of the most common IRRs that have been reported in patients with Fabry disease during REPLAGAL infusions is included in the current version of the REPLAGAL investigator's brochure.

Management of Infusion-Related Reactions

The management of IRRs should be based on the severity of the reaction, and at the discretion of the investigator. If mild or moderate acute infusion reactions occur, medical attention must be sought immediately, and appropriate actions instituted. The infusion can be temporarily interrupted (5 to 10 minutes) until symptoms subside and the infusion may then be restarted, or the infusion rate can be slowed. Some mild and transient effects may not require medical treatment or discontinuation of the infusion.

Shire SHP675-301 Protocol Amendment 6 REPLAGAL[®] (agalsidase alfa)

Oral or IV pretreatment with antihistamines and/or corticosteroids, from 1 to 24 hours prior to infusion, may prevent subsequent reactions in those cases where symptomatic treatment was previously required. Pretreatment of infusion reactions is left to the clinical judgment of the investigator.

If further analysis of IRRs is necessary, additional clinical laboratory samples may be collected at the discretion of the investigator and in consultation with the study medical monitor.

Symptoms of the Disease under Study

Symptoms of the disease under study should not be classed as AEs as long as they are within the normal day-to-day fluctuation or expected disease progression and are part of the efficacy or efficacy data collected in the study. Significant worsening of symptoms should be recorded as an AE.

Preexisting conditions prior to initiation of study medication are described in the medical history, and those that manifest with the same severity, frequency, or duration after drug exposure, are not to be recorded as AEs. However, when there is an increase in the severity, duration or frequency of a preexisting condition, the event must be described in the subject's source documentation.

Clinical Laboratory and Other Safety Assessment

A change in the value of a clinical laboratory parameter, vital sign measure, or ECG assessment can represent an AE if the change is clinically relevant or if, during administration of investigational product, a shift of a parameter is observed from a value in the normative range to a value that is outside the normal range and considered clinically significant, or a further worsening of an already clinically significant value. When evaluating such changes, the extent of deviation from the reference range, the duration until return to the reference range, either while continuing administration or after the end of administration with the investigational product, and the range of variation of the respective parameter within its reference range, should also be considered.

If, at the end of the treatment phase, there are abnormal clinical laboratory (such as hematology panel or clinical chemistry panel), vital sign, or ECG values which were not present at the pretreatment evaluation observed closest to the start of study treatment, further investigations should be performed until the values return to within the reference range or until a plausible explanation (eg, concomitant disease or expected disease evolution) is found for the abnormal values.

The investigator should assess, based on the above criteria and the clinical condition of the subject, whether a change in a clinical laboratory value, vital sign, or ECG parameter is clinically significant and represents an AE.

Appendix 3.2 Collection of Adverse Events

All AEs/SAEs are collected from the time the informed consent document is signed until the defined follow-up period stated in Section 8.1.4. This includes events occurring during the screening phase of the study, regardless of whether or not investigational product is administered.

All AEs/SAEs must be followed to closure (the subject's health has returned to his/her baseline status or all variables have returned to baseline), regardless of whether the subject is still participating in the study. Closure indicates that an outcome is reached, stabilization achieved (the investigator does not expect any further improvement or worsening of the event), or the event is otherwise explained.

Appendix 3.3 Assessment of Adverse Events

Severity Categorization

The severity of AEs must be recorded during the course of the event including the start and stop dates for each change in severity. An event that changes in severity is captured as a new event. Worsening medical conditions, signs or symptoms present prior to initiation of investigational product, must be recorded as new AEs.

For example, if a subject reports mild intermittent dyspepsia prior to initiation of dosing with the investigational product, and the dyspepsia becomes severe and more frequent after first dose a new AE of severe dyspepsia (with the appropriate date of onset) should be documented in the source.

The medical assessment of severity is determined by using the following definitions:

- **Mild:** A type of AE that is usually transient and may require only minimal treatment or therapeutic intervention. The event does not generally interfere with usual activities of daily living.
- **Moderate:** A type of AE that is usually alleviated with specific therapeutic intervention. The event interferes with usual activities of daily living, causing discomfort but poses no significant or permanent risk of harm to the research subject.
- Severe: A type of AE that interrupts usual activities of daily living, or significantly affects clinical status, or may require intensive therapeutic intervention.

Relationship Categorization

A physician/investigator must make the assessment of relationship to investigational product for each AE. The investigator should decide whether, in his or her medical judgment, there is a reasonable possibility that the event may have been caused by the investigational product. If there is no valid reason for suggesting a relationship, then the AE should be classified as "not related". Otherwise, if there is any valid reason, even if undetermined or untested, for suspecting a possible cause-and-effect relationship between the investigational product and the occurrence of the AE, then the AE should be considered "related". The causality assessment must be documented in the source.

The following additional guidance may be helpful:

Table A1 **Adverse Event Relationship Categorization**

Related	The temporal relationship between the event and the administration of the investigational product is compelling enough and/or follows a known or suspected response pattern to that product, and the event cannot be explained by the subject's medical condition, other therapies, or accident.
Not related	The event can be readily explained by other factors such as the subject's underlying medical condition, concomitant therapy, or accident and no plausible temporal or biologic relationship exists between the investigational product and the event.

Outcome Categorization

The outcome of AEs must be documented in the source during the course of the study. Outcomes rercialus are as follows:

- Fatal •
- Not Recovered/Not Resolved •
- Recovered/Resolved
- AE Recovered/Resolved With Sequelae •
- Recovering/Resolving •
- Unknown.

If applicable, action taken (ie, dose increased, dose not changed, dose reduced, drug interrupted, drug withdrawn, not applicable, or unknown) should also be recorded in the source documentation.

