9.6 Safety Analyses

The safety endpoints include:

- AEs
- ADA assessments, including NAbs for samples confirmed positive for ADA
- Clinical laboratory tests (serum chemistry, hematology, and urinalysis)
- Electrocardiography
- Vital signs.

Shire SHP675-301 Protocol Amendment 6 **REPLAGAL**[®] (agalsidase alfa)

17 Feb 2022

All safety analyses will be presented for the safety set. All safety measures including, vital signs, clinical laboratory results (hematology, chemistry, urinalysis), ECG, and ADA (including NAbs) assessments will be summarized descriptively at baseline and for each postbaseline visit. Shift from baseline will be provided, if applicable.

Treatment emergent adverse events (TEAEs) are defined as AEs that start or deteriorate during or after the first dose of investigational product through the safety follow up visit/contact. The number of events, incidence, and percentage of TEAEs will be calculated overall and by system organ class and preferred term at both subject level and adverse event level. TEAEs will be further summarized by severity and relationship to investigational product. Multiple events of the same type will be combined for each subject and, when doing this, the worst severity or outcome for each event type will be presented for the analysis. When calculating event rates, the denominator will be the number of subjects commencing follow-up in the relevant analysis population, irrespective of dropouts during the course of follow-up. Adverse events related to investigational product including IRRs, AEs leading to withdrawal, SAEs, and deaths will be similarly summarized/listed.

9.7 **Other Analyses**

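### Read literally, the AE capture rule and the Section 9.6 TEAE definition can class an AE that eases after first dose as treatment-emergent, against Appendix 3.1, and can inflate event-level totals

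*Combined protocol and SAP*

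**What the plan says.** Four parts of the protocol bear on this.

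- **Capture (Appendix 3.3).** On how grades are dated, it says: "The severity of AEs must be recorded during the course of the event including the start and stop dates for each change in severity". The next sentence reads: "An event that changes in severity is captured as a new event". Neither mentions direction. The sentence after that is about worsening only: "Worsening medical conditions, signs or symptoms present prior to initiation of investigational product, must be recorded as new AEs". The dyspepsia example that follows is also a worsening.
- **Collection window (Appendix 3.2).** The window opens at consent: "All AEs/SAEs are collected from the time the informed consent document is signed". On the period before dosing it adds: "This includes events occurring during the screening phase of the study, regardless of whether or not investigational product is administered". Table 1 places screening and baseline between Day -50 and Day 0, so an AE can be open when dosing begins.
- **Analysis definition (Section 9.6, with near-identical text in the synopsis).** For TEAEs, the text says that they "are defined as AEs that start or deteriorate during or after the first dose of investigational product through the safety follow up visit/contact". Counts are tabulated per subject and per event. Repeated events of one type are combined within a subject, keeping the worst severity or outcome.
- **Appendix 3.1 definition.** Besides events that newly emerge under treatment, it admits "any existing event that worsens in either intensity or frequency following exposure". An existing event that improves does not qualify.

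**The concern.** The capture rule creates a newly dated record at every change of grade, and the analysis rule in Section 9.6 then looks at when an AE starts. If the start date of a severity record is taken as the onset of an event, a subject whose screening AE improves after the first infusion gains a TEAE. A single AE that moves between grades after dosing also adds one to the event total at each move.

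TEAE incidence and event counts are main safety outputs. The study has one arm, so no concurrent control group would carry the same artefact and allow it to be discounted. Infusion-related reactions are summarized in the same way, so a reaction that changes grade is open to the same repeat counting at event level.

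**Working it through.** The plan gives no figure to reproduce. The check sets the definitions against each other, then counts records for constructed AE histories. The histories are hypothetical and are not trial data.

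**Step 1: the definitions side by side.** Take an AE that is moderate on Day -3 and mild from Day 2.

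- Appendix 3.3: two records, the second starting on Day 2.
- Section 9.6, read literally on the second record: it starts after first dose, so it is a TEAE.
- Appendix 3.1: the event existed before exposure and did not worsen, so it is not a TEAE.

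The same AE gets two answers, and the protocol does not say which definition governs.

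**Step 2: counting rules.**

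- *Literal rule:* TEAE events = number of severity records starting on or after Day 0; the subject counts if that number is at least 1.
- *Episode rule:* all contiguous records of one event form one episode. It counts once if it began on or after Day 0, or if a post-dose grade exceeds the pre-dose grade; otherwise it does not count.

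**Step 3: results.**

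| History | Records | Literal: events / subjects | Episode: events / subjects |
|---|---|---|---|
| A: moderate Day -3, mild Day 2 | 2 | 1 / 1 | 0 / 0 |
| B: moderate Day -3, mild Day 2, moderate Day 5, mild Day 9 | 4 | 3 / 1 | 0 / 0 |
| C: all post-dose, mild, moderate, mild, moderate, mild | 5 | 5 / 1 | 1 / 1 |
| D: mild Day -3, severe Day 2 (pattern of the protocol's dyspepsia example) | 2 | 1 / 1 | 1 / 1 |

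A and B show misclassification, which can reach both subject and event counts. Combining within a subject does not remove a subject whose only post-dose records come from the eased event. C shows repeat counting: five events in place of one, but still one subject. D shows that a true worsening is handled alike under both rules.

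**Step 4: would limiting new records to worsening be enough?** In B there is one upward step after dosing (mild to moderate on Day 5), so one post-dose record would remain although severity never exceeded the pre-dose grade. In C there is the onset plus two upward steps, so 1 + 2 = 3 records would remain in place of one. The comparison therefore has to be with the pre-dose level, and the event total needs its own counting rule.

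**Step 5: size per case.** Assuming all 45 planned subjects are dosed and form the safety set, one wrongly counted subject adds 1/45 = 2.2 percentage points to the incidence of that preferred term, if it is that subject's only event of the term. This is an effect per case; it does not estimate the total bias.

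**The case against.** A reader might infer that the plan definitely reports improvement as a TEAE. The documents do not support that. Appendix 3.1 points the other way. The text that elaborates the capture rule in Appendix 3.3 speaks only of worsening. Section 9.6 needs the word *deteriorate* only if *start* means onset of the condition, so it can be read consistently with Appendix 3.1. What stands is an unresolved conflict: the capture sentence is general, and the worsening example illustrates it without narrowing it.

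A reader might also infer that a fluctuating AE is counted several times throughout the safety tables. It is not. The combining rule in Section 9.6 counts the subject once in incidence and worst-severity tables. Only event-level totals are exposed, and even there Section 9.6 does not clearly say whether combining applies.

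A third tempting inference is that the natural rise and fall of Fabry pain, gastrointestinal symptoms or fatigue would be turned into apparent harm. Appendix 3.1 largely prevents this. Disease symptoms within normal fluctuation or expected progression are not AEs, and pre-existing conditions that continue unchanged are not recorded as AEs. The easing problem mainly concerns AEs that arise between consent and first dose, are still open at dosing, and then step down a grade before resolving. Many of these would probably be judged unrelated to treatment.

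Finally, Section 9.1 leaves analysis definitions to a SAP, and Appendix 1.4 leaves data entry to eCRF completion guidelines. Either may contain a linking rule, and its absence from the text reviewed does not show that none exists. But a later rule would still have to resolve a written capture rule that conflicts with a written TEAE definition, and records can be linked reliably only if the eCRF collects the link.

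**Conclusion.** The point holds as a conflict between written rules that can affect safety counts. Under the literal reading, an AE present before dosing that eases afterwards can become a TEAE in both subject and event counts, contrary to Appendix 3.1. A post-dose AE can add one to event totals for each severity record, while subject incidence and worst-severity tables are protected from that repeat counting.

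The size is 2.2 percentage points of preferred-term incidence per misclassified subject among 45 dosed, and up to five events in place of one in history C. This rests on treating each severity record's start date as an event onset and on no linking rule being set elsewhere. The documents give no frequency; given the exclusions in Appendix 3.1 it is probably low. The primary efficacy tests, type I error, power and sample size are unaffected. The correction is worth making because it is specific and cheap, and is best made before AE data are collected.

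**What to change.** 1. **Section 9.6, the synopsis and the SAP:** adopt the Appendix 3.1 worsening criterion. A severity-change record of an event already present before first dose is treatment-emergent only if severity or frequency exceeds the pre-dose level. State whether that level is the last or the worst grade before dosing.
2. **Event-level totals:** count contiguous severity records of one event once, at the worst post-dose severity, and state that the combining rule applies there in this form.
3. **Appendix 3.3:** limit the new-event rule to worsening, or keep it and add a parent-event link on the eCRF. By Step 4, limiting it to worsening does not replace items 1 and 2. The link makes item 2 straightforward to program.

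The cost is wording in the protocol and SAP and at most one field on the AE form. If the link is chosen, the stepwise severity history stays available for listings.

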Data collected in clinical studies to date indicate that REPLAGAL remains safe and well-tolerated during long-term use. As with other intravenous (IV)-administered protein therapeutics, the identified and potential risks of treatment with REPLAGAL include occurrence of infusion-related reactions (IRRs) and potential development of neutralizing antibodies (NAbs) that may compromise efficacy. IRRs are idiosyncratic allergic-type hypersensitivity signs or symptoms experienced by patients during the infusion of REPLAGAL or on the first day of its administration. Infusion-related reactions are the most commonly observed ADRs associated with REPLAGAL. The onset of IRRs generally occurs within the first 2 to 4 months after initiation of treatment with REPLAGAL, although later onset (after 1 year) has been reported. The frequency of these events has decreased over time as the number of infusions increased. The clinical and commercial experience has indicated that IRRs can be mitigated with a combination of infusion-rate control and pretreatment with medications such as antihistamines, antipyretics or low-dose corticosteroids. Cardiac ischemic events and arrhythmias triggered by IRRs have been also reported as risks associated with REPLAGAL treatment in patients with pre-existing cardiac manifestations of Fabry disease. The majority of these events were mild in severity, nonserious and resolved. Cardiac events triggered by IRRs are possibly due to the hemodynamic stress caused by infusion. Lack of efficacy due to development of NAbs against agalsidase alfa remains a potential risk but has not been reported during treatment with REPLAGAL.

CONFIDENTIAL

To date, there is no apparent evidence for a loss of efficacy due to NAbs. Borderline immunoglobulins E (IgE) antibody positivity not associated with anaphylaxis has been reported in clinical studies. Additionally, clinical and postmarketing experience has reflected a safety profile for REPLAGAL that continues to support administration in the home setting.

In summary, the cumulative clinical and postmarketing experience indicates that the benefit-risk profile of agalsidase alfa for the treatment of Fabry disease remains favorable supported by the following:

- A high disease burden with life-threatening/debilitating complications
- Alternative treatments are limited and are also associated with significant adverse reactions

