- Demonstrated benefit in pain reduction, improvement or stabilization of cardiac and renal function, and reduction in accumulation of Gb₃
- Well established safety profile with the main identified risks of IRRs, cardiac events triggered by IRRs, and immunogenicity.

The efficacy profile of REPLAGAL was evaluated in clinical studies and REPLAGAL received initial regulatory approval in the European Union (EU) in 2001 based on reduction of pain in patients with Fabry disease. Additionally, the registration studies evaluated important clinical outcome benefits such as QoL, renal function, cardiac structure, and PD (Gb₃) measures.

The benefit-risk for this study is in alignment with the overall clinical program benefit-risk assessment. Investigators will follow site-specific standards for the mitigation of impact from COVID-19 and will manage any AEs related to COVID-19 per study procedures for the non-c reporting and treatment of AEs.

2.3 **Study Rationale**

Initial approval for REPLAGAT was granted in Canada in 2004. At that time, REPLAGAL was manufactured using an RB technology. In March 2009, Shire submitted a Supplemental New Drug Submission for REPLAGAL manufactured using a new bioreactor method intended to eliminate animal-sourced raw materials from the manufacturing process but approval was not granted. On 10 Feb 2017, REPLAGAL manufactured using the AF process received conditional approval in Canada under a Notice of Compliance with Conditions mandating that efficacy of REPLAGAL be confirmed in patients with Fabry disease. This Phase 3 study will be conducted to fulfill the postmarketing commitment to confirm the efficacy of REPLAGAL in a population of treatment-naïve subjects with a confirmed diagnosis of Fabry disease.

2.4 **Compliance Statement**

This study will be conducted in accordance with this protocol, the International Council for Harmonisation Guideline for Good Clinical Practice E6 (ICH GCP, 1996; E6 R2, 2017), Title 21 of the US Code of Federal Regulations (US CFR), the EU Directives (2001/20/EC; 2005/28/EC), and applicable national and local regulatory requirements.

The responsibilities of the study sponsor and investigator(s) are described fully in Appendix 1.

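### The Related row of Table A1 conflicts with the causality rule above it, so an adverse event with both a plausible product link and a disease explanation fits neither category

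*Combined protocol and SAP*

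**What the plan says.** Appendix 3.3 (Relationship Categorization) asks the investigator whether "there is a reasonable possibility that the event may have been caused by the investigational product". With no valid reason to suggest a link, the AE is not related. Otherwise it is related "if there is any valid reason, even if undetermined or untested, for suspecting a possible cause-and-effect relationship between the investigational product" and the event. Under this rule a competing explanation does not remove the related label.

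Table A1 follows, introduced by "The following additional guidance may be helpful". It has two rows:

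- **Related** needs compelling timing and/or a known or suspected response pattern, and also that "the event cannot be explained by the subject's medical condition, other therapies, or accident".
- **Not related** needs a ready explanation by other factors, and also that "no plausible temporal or biologic relationship exists between the investigational product and the event".

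The label is used elsewhere. Appendix 3.1 defines an IRR as an AE that starts during the infusion or within 24 hours after its start and "is judged as related to study treatment". Section 9.6 summarizes treatment-emergent AEs (TEAEs) by relationship, and also related AEs including IRRs. Section 2.2 reports: "Cardiac ischemic events and arrhythmias triggered by IRRs have been also reported as risks associated with REPLAGAL treatment in patients with pre-existing cardiac manifestations". Its benefit-risk summary reads: "Well established safety profile with the main identified risks of IRRs, cardiac events triggered by IRRs, and immunogenicity". Section 2.1 counts arrhythmia among the manifestations of Fabry disease, and inclusion criterion 9 (Section 5.1) requires LVH in every subject.

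**The concern.** The rule and the table guide the same two-way decision but set different tests. The rule asks only whether there is reason to suspect the product. The Related row also asks that nothing else could explain the event. They part where an event has both a product link and a disease explanation, and in this trial that overlap is foreseeable. The product has an identified cardiac risk during infusion, the disease itself causes arrhythmia, and every subject has a hypertrophied ventricle.

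Several things depend on the call:

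- whether an event counts as an IRR (Appendix 3.1);
- the TEAE-by-relationship, related-AE and IRR summaries (Section 9.6);
- the SUSAR definition (Appendix 3.1) and notification of related, unexpected SAEs (Appendix 3.11);
- the home-infusion conditions, which turn on treatment-related SAEs and moderate or severe IRRs (Section 6.2.1);
- the option to omit post-infusion observation and vital signs when the first 3 infusions pass without an IRR (Sections 6.2.1 and 8.2.3.5).

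No view is taken here on those clinical conditions, only that the label they use needs a single definition. The trial is single-arm (Section 4.1), has no data monitoring committee (Section 9.2) and may run at up to 50 sites (Section 4.5). There is therefore no concurrent control rate to set against the investigators' causality calls, and sites could read the two texts differently.

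**Working it through.** The plan states no figure on this point, so the check is one of logic. Let R mean that there is a reason to suspect the product (timing or a known pattern). Let E mean that the medical condition or another factor can explain the event. Each combination is classified under the rule and under Table A1.

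| Case | R | E | Rule in Appendix 3.3 | Table A1 |
|---|---|---|---|---|
| 1 | yes | no | related | Related |
| 2 | no | yes | not related | Not related |
| 3 | yes | yes | related | neither row |
| 4 | no | no | not related | neither row |

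- **Cases 1 and 2:** rule and table agree.
- **Case 3:** the event fails the Related row because E is true. It fails the Not related row because a plausible temporal or biologic link exists.
- **Case 4:** the event fails the Related row for want of R. It fails the Not related row because nothing else readily explains it.

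The two texts diverge in 2 of 4 cases. In neither does the table give the opposite label; it gives none. The rule covers all four cases.

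Using the same R for both texts is generous to the table. Its Related row asks for compelling timing or a recognized pattern, whereas the rule accepts any valid reason, even an untested one.

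The arrhythmia during infusion in a subject with LVH falls in case 3 if the investigator thinks the heart disease could explain it. R comes from the timing and from the risk in Section 2.2. E comes from Section 2.1 and criterion 9.

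The size cannot be worked out. With 45 subjects (Section 9.3) and 53 infusions each (Section 6.2.1), the largest denominator is 45 × 53 = 2,385 infusions. That assumes no attrition, while Section 9.3 expects about 20% of subjects not to qualify for the completers set. A count of affected events would also need the rate of infusion-associated cardiac events and the share of investigators who would follow the table over the rule. The documents give neither.

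**The case against.** The strongest reply is that the table does not govern. It is offered as optional help beneath an operative rule that already calls a case 3 event related, so an event the table leaves unclassified falls back to the rule. This stands, and it limits the consequence to sites that apply the table instead. It does not excuse guidance that contradicts the rule it is meant to explain.

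A reader might infer that the table sets the opposite standard, or that almost no cardiac event could be called related because every subject has LVH. The documents support neither reading. The Not related row also excludes a case 3 event, so the table leaves a gap and does not reverse the label. Having LVH is also not the same as LVH explaining a particular event; that remains a medical judgment. Further, Section 2.2 describes cardiac events triggered by IRRs. LVH does not readily explain an allergic-type reaction, so the triggering IRR can be related under either text. The ambiguity is confined to the cardiac event.

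Safeguards that do not depend on relatedness also stand. Section 9.6 tabulates all TEAEs overall and by system organ class and preferred term. Appendix 3.5 sends all SAEs to the sponsor within 24 hours whatever their relationship. A SUSAR must also be unexpected against the investigator's brochure, which is not among the documents, so an effect on SUSAR reporting cannot be verified.

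**Conclusion.** The conflict is real and can be read directly from the text: rule and table diverge in 2 of 4 logical cases. The case that matters is where the product's identified cardiac risk may fall in an all-LVH population.

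The consequence is conditional. Sites that follow the table could leave such events out of the related-AE and IRR summaries, and the same label feeds the SUSAR definition and the home-infusion conditions. A reader might go further and conclude that the table would keep the cardiac risk out of the safety results. That does not follow, because the rule already labels these events related, and any event recorded as an AE stays in the overall TEAE data and, if serious, in the SAE data.

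The number of events affected cannot be derived. The primary endpoints and the sample size are not touched. The conclusion assumes only that some investigators will use the table as their working definition.

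**What to change.** Reconcile Table A1 with the rule above it:

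- **Related row:** delete the condition that "the event cannot be explained by the subject's medical condition, other therapies, or accident", together with the word that joins it to the rest of the row. Make clear that the remaining wording on timing and response pattern illustrates a valid reason and does not set a higher bar.
- **Not related row:** define it as no valid reason to suggest a relationship, as the rule does.

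The two rows then cover all four cases, and an alternative explanation alone no longer removes the related label. Do not add wording that the product contributed to the event. The rule asks whether the product may have caused it, and a contribution test would be a new standard.

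The cost is a short edit to one table in the next amendment and brief site retraining. Reported related-AE and IRR rates may be somewhat higher. Sample size and efficacy analyses do not change.
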